6.3 Study population

6.3.1 Inclusion Criteria

Patients who meet the following criteria will be considered eligible to participate in the clinical trial:

1. Patients with either newly diagnosed CUA OR recurrent CUA that has been dormant with no skin lesion involvement for at least 90 days from study start (new or recurrent diagnosis must be made within 5 weeks of study start)
2. Patients who signed the written informed consent to participate in this clinical trial (prior to any clinical trial-related procedures being performed), after reading the Patient Information Sheet and Informed Consent Form (ICF), and who had the opportunity to discuss the clinical trial with the Investigator or designee
3. Males or females aged ≥ 18
4. Patients on maintenance haemodialysis
5. Patients with at least a minimum level of pain on VAS scale or on pain-killers stronger than NSAIDs
6. Females of child-bearing potential should use a highly effective contraceptive measure throughout the study AND have a negative serum pregnancy test at entry. Male patients having sexual relationship in which pregnancy can occur should take adequate contraceptive precautions (wear a condom).

6.3.2 Exclusion Criteria

Patients who meet one or more of the following criteria will not be considered eligible to participate in the clinical trial:

1. Body weight above 150 kg
2. BMI > 35 and central (abdominal) ulcers
3. History of bisphosphonate treatment within 12 months before entering into the study
4. Severely ill patients without reasonable expectation of survival for > 6 months according to the treating physician
5. Patients with scheduled parathyroidectomy during the run-in or study period
6. Female patients who are either intending to get pregnant or are undergoing treatment to get pregnant, as well as breast-feeding females
7. Participation in another clinical trial with an experimental drug within 90 days prior the inclusion
8. Any psychological, emotional problems, any disorders or resultant therapy that is likely to invalidate informed consent, or limit the ability of the patient to comply with the Clinical Trial Protocol requirements
9. Patients who, in the opinion of the Investigator, are considered unsuitable for any other reason

6.3.3 Criteria for subject withdrawal

A subject is defined as having entered the clinical trial when he/she has provided written informed consent. A withdrawal is a subject who receives a study subject code and for whom treatment is prematurely terminated for any reason.

Possible reasons for withdrawal of a subject from the clinical trial:

- Adverse Event(s)
- Subject lost to follow-up
- Withdrawal of consent
- Pregnancy
- Death
- Other (specify)

6.4 Sample size

Given the exploratory purpose of the study, the sample size will not be recalculated.

The original sample size justification was:

Based on recent historical data from a U.S. large dialysis provider organization, approximately 25% of calciphylaxis skin lesions are considered to be improved over a 3-6-month period (data unpublished; personal communication). A total of 15 subjects was determined necessary to show with 80% power that the percentage of subjects for which the primary ulcer is totally or partially healed after 12 weeks of treatment is greater than 25%. For these calculations, it was assumed that the percentage of totally or partially healed subjects for SNF472 will be 60%.

6.5 Randomization and blinding

This was an open-label, single-arm study with no randomization. Efforts to minimize assessment bias were implemented by including an independent review of the images. A protocol for the review and scoring of the images was produced.

6.6 Study methods

6.6.1 Bates-Jensen Wound Assessment Tool (BWAT)

The Bates-Jensen Wound Assessment Tool (BWAT) score is collected through a questionnaire of 13 items, which are evaluated individually with a score of 1 to 5. BWAT is summarized by a total score which is calculated by adding up the scores of all individual items. Therefore, the total score ranges from 13 to 65 and can be only calculated if all items are answered. However, for the purpose of this analysis missing items were imputed as described in Section 8.4. Note that the BWAT contains two extra variables to indicate the location and shape of the lesion that are not used for the calculation of the total score.

6.6.2 Independent Image Review

Standardized lesion images were evaluated by two independent reviewers. The independent reviewers evaluated all images and assessed the evolution of the lesions compared to Week 1 by indicating if the lesion improved, worsened or did not change.

The assessment was performed in two separate steps in the following order:

1. Blinded Review: reviewers compared Week 1 to Week 12 on a blinded manner without knowing the order of the visits.
2. Unblinded Review: reviewers assessed the evolution of the lesions (primary, secondary, and tertiary) for all visits comparing them to Week 1.

For any discordant scores, the evaluators had to discuss and try to find agreement. In situations where concordance could not be reached, the worst result will be used for the analysis.

6.6.3 Pain Visual Analog Scale (VAS)

A VAS is a measurement instrument that aims to measure a characteristic or attitude that is believed to range across a continuum of values and cannot easily be directly measured.

6.6.4 Wound Quality of Life (Wound-QoL)

The Wound-QoL measures the disease-specific, health-related quality of life of subjects with chronic wounds. It consists of 17 items on impairments which are always assessed in retrospect to the preceding seven days. Answers to each item are coded with numbers (0='not at all' to 4='very much').

A Wound-QoL global score on overall disease-specific quality of life is computed by averaging all items. A global score can only be computed if at least 75% of the items have been answered (i.e., at least 13 in 17 items are valid). Otherwise, the global score will be considered missing.

In addition, subscales of the Wound-QoL can be calculated representing different dimensions of disease specific quality of life by averaging the respective items. A subscale can only be computed if no more than 1 item of the subscale is missing.

The items are assigned to subscales as follows:

- Subscale 'Body': Items #1 to #5
- Subscale 'Psyche': Items #6 to #10
- Subscale 'Everyday life': Items #11 to #16

Item #17 does not belong to any of the subscales.

7. SEQUENCE OF PLANNED ANALYSES

7.1 Interim analysis

An interim analysis is planned when approximately 50% subjects have completed 12 weeks of treatment. The objective of this interim analysis is to determine whether the study should continue to enroll subjects, given the difficulty in finding qualifying subjects. The interim analysis will also be used to help inform the design of future clinical trials in this population.

7.2 Final analysis

The final analysis will be performed when all subjects have finished the study and the database has been successfully locked.

8. STATISTICAL METHODS

8.1 General considerations

██ Statistical analyses will be reported with tables, figures, and subject data listings and presented in rich text format and pdf. Output specifications for all tables, listings and figures will be in conformance with guidelines specified by the International Council on Harmonisation (ICH E3). In general, continuous variables in demographic and baseline characteristics will be summarized by displaying: n (non-missing sample size), mean, standard deviation (SD), standard error (SE), median, quartiles, maximum and minimum. The frequency and percentages (based on the non-missing sample size) of observed levels will be reported for all categorical measures. Percentages will be calculated out of the total number of subjects in the analysis set or the nonmissing sample size, as appropriate.

Numerical efficacy variables will be summarized displaying n, mean, 95% confidence interval, median, SD, SE, quartiles, minimum, maximum.

Time-to-event variables will be calculated and analyzed in days if not specified otherwise.

All summary tables will be structured in a column and will be annotated with the total population size relevant to that table/treatment, including any missing observations.

Differences within groups will be assessed using paired t-test or Wilcoxon test as considered appropriate.

No inferential statistics will be applied to baseline characteristics and safety variables unless specified otherwise.

In general, all data recoded in this study will be listed, sorted by site and subject, and when appropriate by visit number (or assessment date). A description of the content and format of all planned listings is provided in the Appendix, Section 12.2.

Report summaries will be generated using validated SAS® software, version 9.3 or higher, on a PC platform. Additional validated software may be used to generate analyses, as needed.

All SAS programs that create outputs or supporting analysis datasets will be validated by a second statistical programmer or biostatistician. At a minimum, validation of programs will consist of a

review of the program log, review of output or dataset format and structure, and independent review of all outputs.

8.2 Analysis populations

8.2.1 All Subjects

Subjects included in the study who have signed informed consent and received at least one dose of SNF472.

8.2.2 Safety Analysis Set

Subjects included in the study who have signed informed consent and received at least one dose of SNF472.

8.2.3 Efficacy Analysis Set

The definitions given in the protocol about the efficacy analysis sets were considered very restrictive, therefore two new analysis sets for efficacy have been defined:

8.2.3.1 *Intention to Treat Set*

Subjects who have received at least one dose of SNF472 and for whom at least one post-baseline efficacy measurement is obtained.

8.2.3.2 *Per Protocol Set*

The Per Protocol Set includes all subjects who receive at least 75% of SNF472 doses and who did not violate the protocol in a way that might affect the evaluation of the effect of the study drug on the primary endpoint.

Major and minor protocol violations will be identified and documented by the Sponsor.

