### 9.2. General Considerations

All efficacy (ulcer size, Bates-Jensen Wound tool assessments, pain scale, and wound QoL), PK and safety parameters as well as population characteristics will be listed and described using summary statistics. Descriptive statistics (n, mean, standard deviation, median, minimum, and maximum) will be calculated for each quantitative variable (unless otherwise stated). Frequency counts (number of subjects [n] and percentages) will be made for each qualitative variable.

All listings will be sorted by patient number, time-point, and parameter (if applicable).

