5.2.2 Secondary endpoints

Wound healing:

- Absolute change from baseline in BWAT total and component scores by visit for the primary lesion, secondary lesion, and tertiary lesions.
- Qualitative change from baseline in imaging score by visit for the primary lesion, secondary lesion, and tertiary lesions.

Pain:

- Absolute change from baseline by visit in the Pain Visual Analog Scale (VAS).

Quality of Life:

- Absolute change from baseline at Weeks 6 and 12 in global score and subscales of wound QoL score.

Wound and disease complications:

- Presence/absence of new wound infection at any time post baseline
- Presence/absence of new systemic infection at any time post baseline
- Surgical treatment of the wound at any time post baseline
- Requires or prolongs hospitalization
- Death

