8.2.4 PK Analysis Set

All subjects who receive at least 1 dose of SNF472 and for whom either of the primary PK parameters (C_{max}) can be calculated. Further analysis sets might be defined if considered appropriate to assess the sensitivity of the PK results, e.g., subjects without any major protocol deviation thought to interfere with the absorption, distribution, metabolism, and excretion of the compound to be measured.

The following table indicates the correspondence between the above defined analysis sets and the planned statistical analysis:

Planned analysis / Analysis sets	All Subjects*	Safety*	Intention to treat	Per Protocol	PK
----------------------------------	---------------	---------	--------------------	--------------	----

Disposition, Protocol Deviations and Analysis Sets	X				
Baseline and disease characteristics		X			
Previous and Concomitant medications		X			
Treatment compliance and exposure		X			
Primary endpoint			X	X	
Secondary endpoints			X		
Safety variables		X			
PK analysis					X
PD/Biomarker analysis					X
Subgroup analysis			X		
All subject listings	X				

* Includes all patients who received at least 1 dose.

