9.2.3 Hospitalization and Death

Hospitalizations will be identified from the list of Adverse Event for which Seriousness has been reported as “Requires or prolongs hospitalization”.

The number and percentage Hospitalizations will be summarized by System Organ Class and Preferred Term presenting the number of events, the number of subjects and percentage (Shell T-5).

Deaths will be identified from the list of adverse events, for which Seriousness has been reported as “Results in death” or Outcome has been reported as ”Death” or Primary Reason for Premature Termination has been reported as “Death” on the End of Study CRF section.

The number and percentage of deaths will be computed and will be summarized by System Organ Class and Preferred Term (Shell T-5).

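### A dosed patient who dies before any post-baseline score drops out of the death endpoint, because secondary endpoints are assigned to the Intention to Treat set only

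*SAP*

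**What the plan says.** SAP 5.2.2 has a group of secondary endpoints for wound and disease complications. It contains new wound infection, new systemic infection ("Presence/absence of new systemic infection at any time post baseline"), surgical treatment of the wound, hospitalisation ("Requires or prolongs hospitalization") and death.

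The table at the end of SAP 8.2.4 "indicates the correspondence between the above defined analysis sets and the planned statistical analysis". Its row for secondary endpoints is marked under Intention to Treat and under no other set. Safety variables are marked under the Safety set.

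The two sets differ in one condition. The Safety Analysis Set (SAP 8.2.2) needs consent and one dose. The Intention to Treat set (SAP 8.2.3.1) is "Subjects who have received at least one dose of SNF472 and for whom at least one post-baseline efficacy measurement is obtained".

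On the analysis of deaths, SAP 9.2.3, which sits inside the efficacy section, says: "The number and percentage of deaths will be computed and will be summarized by System Organ Class and Preferred Term". Neither 9.2.3 nor 9.2.2.5 (wound complications) names an analysis set or a denominator.

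**The concern.** Read together, these sections make membership of the analysis set depend on having lived long enough to be scored, and death is one of the endpoints analysed in that set. A patient who is dosed and dies before the first post-baseline score is excluded because of the event that the endpoint is meant to count.

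Two things are at stake. The death endpoint can be biased low. It can also disagree with the Safety-set table of adverse events leading to death (SAP 9.3.1), with no rule saying which figure is the endpoint. In a trial of about 15 patients, one patient is enough to produce both effects.

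**Working it through.** The plan states no expected death rate or precision for this endpoint, so there is no figure of its own to reproduce. The sample size in SAP 6.4 concerns healing and does not bear on this point.

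**Step 1: which measurement opens the set.** The SAP does not define an efficacy measurement. Protocol 9.2 gives a list: "All efficacy (ulcer size, Bates-Jensen Wound tool assessments, pain scale, and wound QoL". Death, hospitalisation and infection are not on it. BWAT, VAS and images are next due after baseline at Week 2 Day 1 (schedules in both documents), 7 days after first dose. Wound QoL is next due at Week 6. The exposed window is therefore about 7 days for a patient who attends as scheduled.

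**Step 2: effect of one excluded death.** With k deaths among n dosed patients, removing one patient who died changes k/n to (k − 1)/(n − 1). This is lower whenever k < n, because (k − 1)n < k(n − 1) reduces to k < n. With n = 15 and one death before any score (numbers of deaths assumed; Clopper-Pearson 95% intervals):

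| Total deaths | All dosed | Intention to Treat |
|---|---|---|
| 1 | 1/15 = 6.7% (0.2 to 31.9) | 0/14 = 0.0% (0 to 23.2) |
| 2 | 2/15 = 13.3% (1.7 to 40.5) | 1/14 = 7.1% (0.2 to 33.9) |
| 3 | 3/15 = 20.0% (4.3 to 48.1) | 2/14 = 14.3% (1.8 to 42.8) |

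**Step 3: effect on the other events.** If the excluded patient did not have the event, only the denominator shrinks: 3/15 = 20.0% becomes 3/14 = 21.4%. A patient who dies early without a wound infection therefore raises the wound infection rate by leaving the set. One who was infected first lowers it.

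**Step 4: how likely an early death is.** Inputs: one-year survival of 45% (Protocol 2.2), 15 dosed patients, and a constant hazard, which is my assumption.

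- Per patient, within 7 days: 1 − 0.45^(7/365) = 0.0152.
- Expected among 15: 15 × 0.0152 = 0.23.
- At least one among 15: 1 − (1 − 0.0152)^15 = 0.205.
- With 50% one-year survival instead (Protocol 4.3 puts one-year mortality at about 50%): 0.181.
- Over the 12 weeks, for scale: 1 − 0.45^(84/365) = 0.168 per patient, or about 2.5 deaths among 15.

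The hazard could be off in either direction. Protocol 2.2 says the survival gap is widest in the first months after diagnosis, which would raise the figure. Protocol 5.4 excludes patients without a reasonable expectation of surviving more than 6 months, which would lower it.

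**The case against.** **The early death is not hidden.** This stands. SAP 9.3.1 tabulates adverse events leading to death and serious adverse events for all dosed subjects. Disposition and the listings also cover every dosed subject. A reader might infer that a death could vanish from the report, and the documents do not support that. What goes wrong is the endpoint and its agreement with the safety table.

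**Patients who leave alive are mostly kept.** This also stands. Protocol 5.5 and 8.2.5 ask for an End of Study Visit after withdrawal, with the Follow-Up assessments, and Protocol 8.2.4 includes pain and lesion scores among these. One score is enough for membership, so neither an early withdrawal nor a missed Week 2 visit excludes anyone by itself. The same holds for a patient who is hospitalised, infected or operated on and is scored later.

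**The intended set is not beyond doubt.** This stands in part. SAP 9.2.3 is numbered outside 9.2.2, draws on adverse event data and uses the same table shell as the adverse event tables. One could also argue that a recorded death is itself an efficacy measurement. But the only explicit assignment is the table in 8.2.4, nothing in 9.2.2.5 or 9.2.3 overrides it, and Protocol 9.2 points against the wider reading. If another set is meant, the SAP has to say so.

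**Little rests on the number.** There is no control arm and no test on deaths, and SAP 6.4 and 8.7 call the study exploratory and proof of concept. That limits the consequence, but it does not make the endpoint correct as defined.

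**Conclusion.** The point holds for death. On the plain reading of SAP 5.2.2, 8.2.3.1 and 8.2.4, a dosed patient who dies before any post-baseline efficacy measurement is removed from the death endpoint, and the reported rate falls. One such patient among 15 moves it by about 6 to 7 percentage points in the examples above, well inside the confidence intervals at this sample size. Under the constant-hazard assumption there is roughly a one-in-five chance that at least one patient is affected, so on the same model about 79% of such trials would have no death in the window.

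Two stronger readings are tempting and fail:

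- That the bias always favours SNF472. Losing a patient without the event raises the rate, so for hospitalisation, infection and surgery the direction depends on who is lost.
- That the chance of the problem is about 50%, because the next scores after Week 2 come at Week 4, 21 days after first dose. The model does give 1 − 0.45^(15 × 21/365) = 0.498, but that is the chance that any of 15 patients dies by day 21. It equals the chance of exclusion only if all 15 miss Week 2. If 10% miss it (assumed), the per-patient risk is 0.0152 + 0.10 × (0.0449 − 0.0152) = 0.0182, and the chance of at least one is about 24%.

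**What to change.** Split the secondary endpoints row of the table in SAP 8.2.4. Keep BWAT, imaging, VAS and Wound-QoL on the Intention to Treat set. Assign death, hospitalisation, wound infection, systemic infection and wound surgery to the Safety Analysis Set. State in 9.2.2.5 and 9.2.3 that the denominator is all dosed subjects.

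The Safety set already exists, no new data are needed, and these events do not require a paired score. The death endpoint and the table of adverse events leading to death would then share one denominator. The cost is one changed table row and a sentence in each of two sections; the stated event rates may become slightly less favourable.

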8.2.4 PK Analysis Set

All subjects who receive at least 1 dose of SNF472 and for whom either of the primary PK parameters (C_{max}) can be calculated. Further analysis sets might be defined if considered appropriate to assess the sensitivity of the PK results, e.g., subjects without any major protocol deviation thought to interfere with the absorption, distribution, metabolism, and excretion of the compound to be measured.

The following table indicates the correspondence between the above defined analysis sets and the planned statistical analysis:

Planned analysis / Analysis sets	All Subjects*	Safety*	Intention to treat	Per Protocol	PK
----------------------------------	---------------	---------	--------------------	--------------	----

Disposition, Protocol Deviations and Analysis Sets	X				
Baseline and disease characteristics		X			
Previous and Concomitant medications		X			
Treatment compliance and exposure		X			
Primary endpoint			X	X	
Secondary endpoints			X		
Safety variables		X			
PK analysis					X
PD/Biomarker analysis					X
Subgroup analysis			X		
All subject listings	X				

* Includes all patients who received at least 1 dose.

8.3 Covariates and subgroups

The primary efficacy endpoint will be summarized by various subgroups of interest based on baseline and demographic categories including age (e.g., < 65 years of age and \geq 65 years of age), gender, race, and country, and based on certain medications (e.g. STS: sodium thiosulfate). Summaries by subgroup will only be produced if there are at least 2 subjects in the category of interest. Otherwise, categories might be grouped as appropriate.

8.4 Missing data

This section provides a general description about methods used to impute missing data. Specific details for imputed variables will be given in Section 9.2.

Missing imputation will be only applied for the primary and key secondary endpoints, i.e. BWAT, VAS and Wound QoL. The main analysis will be based on Multiple Imputation (MI). Sensitivity analyses will be conducted to assess the robustness of the results with regards to handling of missing data. The following methods will be applied: Last Observation Carried Forward (LOCF), and Observed Cases (OC) (Molenberghs & Kenward, 2007).

Multiple Imputation

Multiple imputation was selected as the method for imputing missing data as the natural progression of calciphylaxis skin lesions under standard of care treatment varies considerably [Nigwekar et al, 2013]. Rather than making assumptions under the LOCF method that may either be too optimistic or conservative relative to the natural progression of skin lesions under standard

of care treatment, multiple imputation uses all available data for a given variable to impute for missing data. Missing data will be imputed 100 times to generate 100 complete data sets, using the MI SAS procedure (using *Markov Chain Monte Carlo (MCMC)* for continuous variables or the *Fully Conditional Specification (FCS) Discriminant* analysis for categorical variables). The absolute change from baseline at Week 12 will be then derived from observed and imputed data at this time point. The 100 complete data sets will be then analyzed using a paired t-test, and the MIANALYZE procedure will be used to generate valid statistical inferences by combining results from the 100 analyses using Rubin's formulae.

The number of imputations (100) will be informally verified by replicating sets of 100 imputations and checking whether the combined results are stable. If not stable, the number of imputations will be increased and informally checked as above, and thus until stable estimates are obtained.

The imputation model will include:

- The endpoint values from all non-missing scheduled weeks.
- The endpoint values from other items within the same scale, if applicable.

LOCF

This analysis imputes the last measured value of the endpoint to all subsequent evaluations. In case of missing data at baseline, the missing value will be imputed using the first available visit, i.e., First Observation Carried Backward, FOCB.

Observed Cases

The analysis under this scenario will be conducted without any missing data imputation.

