6. STUDY DESIGN

6.1 General study design and plan

It is an open-label single-arm clinical trial. Up to 15 CUA subjects will be enrolled, treated, and followed over a 12-week period to assess the safety and efficacy of SNF472 for the treatment of CUA.

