9.2 Efficacy Analysis

9.2.1 Primary endpoint

The primary endpoint is the absolute change in BWAT total score between baseline (Week 1) and Week 12 for the primary lesion (the largest one).

Absolute change from baseline will be calculated as differences in the total score from Week 1 to Week 12. Descriptive statistics will be presented. Differences between the two visits will be analyzed using a Paired Student's T-Test. (Shell T-7)

Missing imputation will be done on the item level. For the imputation of baseline missing item scores FOCB will be used for LOCF imputation method if any subsequence item score is available, else the score will be imputed by 3. For the multiple imputation method the baseline values will be imputed by 3. The main analysis will be done using Multiple Imputation, and supported by the different sensitivity analysis as specified in Section 8.4. A forest plot summarizing these results will be produced presenting the estimated change from Week 1 to Week 12 and its 95% confidence interval for the different imputation methods (Shell F - 1).

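### Unless SAP 8.4 supplies the complete-data degrees of freedom, the pooled 95% CI for the primary endpoint uses about 1.96 where a paired t-test in 15 subjects needs 2.145

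*SAP*

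**What the plan says.** SAP 8.4 sets the main method for missing data: "The main analysis will be based on Multiple Imputation (MI"). The steps are as follows.

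- "Missing data will be imputed 100 times to generate 100 complete data sets".
- "The 100 complete data sets will be then analyzed using a paired t-test".
- Finally, "the MIANALYZE procedure will be used to generate valid statistical inferences by combining results from the 100 analyses"; the sentence ends by naming Rubin's formulae.

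SAP 9.2.1 applies this to the Week 1 to Week 12 change in BWAT total score: "The main analysis will be done using Multiple Imputation, and supported by the different sensitivity analysis as specified in Section 8.4". It also plans a forest plot with a 95% CI for each imputation method. SAP 9.2.2.3 and 9.2.2.4 use the same approach for VAS and Wound-QoL, and SAP 9.7 carries the imputation into the subgroup summaries.

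On numbers, SAP 6.1 says "Up to 15 CUA subjects will be enrolled, treated, and followed over a 12-week period". The analysis set in SAP 8.2.3 is "Subjects who have received at least one dose of SNF472 and for whom at least one post-baseline efficacy measurement is obtained".

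Neither document states the reference df for the pooled result, a complete-data df, or whether a small-sample adjustment is used. Neither gives an expected amount of missing Week 12 data.

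**The concern.** Rubin's original pooled df depend on the number of imputations and on the share of variance due to missing data. They take the complete-data sample as infinitely large. With 100 imputations and about 15 subjects, that assumption drives the result: the pooled statistic is referred to what is in effect a normal distribution, although each of the 100 analyses is a t-test on about 14 df. MIANALYZE makes the small-sample adjustment only if the complete-data df are passed to it. Followed as written, the text omits them.

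At stake are the main CI and p-value of the primary endpoint, and those of VAS and Wound-QoL. The forest plot is also affected. Its LOCF and observed-case rows come from ordinary paired t-tests with t quantiles, and the MI row would use a different reference distribution. Rows meant to show robustness to missing data would then differ partly for a reason unrelated to missing data. The check in SAP 8.4 on the number of imputations does not help, because the unadjusted df grow in proportion to m - 1.

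**Working it through.** **The plan's own figure.** The SAP gives no figure for this step. Its only power statement (15 subjects, 80% power, 25% against 60%; SAP 6.4) concerns a responder endpoint. It reproduces approximately: an exact binomial rule of at least 8 responders in 15 has power 78.7%. It has no bearing on the pooling.

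**Inputs.** From SAP 8.4, m = 100. From SAP 6.1, n = 15 if all are analysed, so the complete-data df are 15 - 1 = 14. The confidence level is 95%, two-sided (SAP 9.2.1). The share of pooled variance due to missing data, λ, is not in the documents; it is assumed here to lie between 0.10 and 0.30.

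**Step 1: no missingness assumption needed.** As λ approaches 0, Rubin's df go to infinity and the multiplier is 1.960. A t-test on 14 df needs 2.145.

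- Narrowing: 1 - 1.960/2.145 = 8.6%.
- Two-sided error: 2 × P(T on 14 df > 1.960) = 7.0%.

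**Step 2: with missing information.**

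- Rubin: df = (m - 1)/λ² = 99/λ².
- Barnard-Rubin: df_obs = (15/17) × 14 × (1 - λ), then df = 1/(1/df_Rubin + 1/df_obs).
- Narrowing = 1 - t_Rubin/t_BR.
- Analytic error = 2 × P(T on the Barnard-Rubin df > t_Rubin).

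| λ | Rubin df | t | Barnard-Rubin df | t | CI narrower by | analytic error |
|---|---|---|---|---|---|---|
| 0.10 | 9,900 | 1.960 | 11.1 | 2.198 | 10.8% | 7.6% |
| 0.20 | 2,475 | 1.961 | 9.8 | 2.233 | 12.2% | 7.9% |
| 0.30 | 1,100 | 1.962 | 8.6 | 2.279 | 13.9% | 8.3% |

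Over the same λ range, the narrowing is 14.2-18.1% for n = 12 and 8.8-11.3% for n = 18.

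**Step 3: does the error really reach 8%?** The last column assumes that the pooled statistic follows a t distribution with exactly the Barnard-Rubin df. Simulation tests that. Settings: n = 15, normal total scores at baseline and Week 12, Week 12 values missing completely at random, proper Bayesian normal imputation, m = 100.

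| Week 12 values missing | Unadjusted, 8,000 replicates | Unadjusted, 5,000 replicates | Barnard-Rubin, 5,000 replicates |
|---|---|---|---|
| 0 | about 7% | 6.7% | 4.5% |
| 1 | 6.6% | 6.6% | 4.3% |
| 2 | 6.2-6.7% | 6.4% | 4.2% |
| 3 | 6.3-6.4% | 6.7% | 4.2% |
| 4 | 5.5-6.2% | 5.9% | 3.3% |
| 5 | 5.5-5.8% | not run | not run |

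The Monte Carlo standard error is about 0.3 points with 8,000 replicates and √(0.065 × 0.935/5,000) = 0.35 points with 5,000. The 5,000-replicate runs used a baseline to Week 12 correlation of 0.5. The unadjusted error is flat or falls as more values are missing, the opposite of the analytic column. Imputation that draws its parameters from so few subjects already inflates the pooled variance, which offsets part of the short multiplier.

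**Step 4: smaller sets.** SAP 8.3 allows subgroup summaries with as few as 2 subjects, and SAP 8.1 gives numerical efficacy variables a 95% CI. If those intervals come from pooling without complete-data df and λ is near 0, the narrowing is 1 - 1.96/2.776 = 29% for n = 5 and 1 - 1.96/12.7 = 85% for n = 2.

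**The case against.** The strongest reply is that this is silence, not error. SAP 8.4 neither sets nor excludes the complete-data df, and a programmer may well supply them. That stands, and the point is therefore conditional. It does not dispose of the matter: Rubin's formulae as named do not contain n, so the plain reading gives 1.96, and a reader cannot tell which interval will be reported.

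The second reply is that the recommended interval is not exact either. Barnard-Rubin df ran below the nominal 5% in the simulation, so the 11-14% is measured against an interval that is itself somewhat too wide. That also stands. The 8.6% at negligible missing information does not depend on it.

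The third is that the study is a proof of concept without multiplicity adjustment (SAP 8.7), with no alpha or success criterion for the BWAT test. LOCF and observed-case results with ordinary t quantiles are reported alongside. This lowers the severity. It does not remove the point, because MI is designated the main analysis.

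Three stronger readings are tempting but unsupported.

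- **The test runs at about 8%.** That is the analytic value for an assumed λ, and simulation does not bear it out.
- **The MI row will look more precise only because the other rows use t quantiles.** MI also adds between-imputation variance, while LOCF treats carried-forward values as observed. In the 5,000-replicate simulation the unadjusted MI interval matched LOCF with 2 values missing and was 6% and 12% wider with 3 and 4. It was 7-9% narrower than observed cases, but those also use fewer subjects.
- **The interim error is 12-14%.** SAP 7.1 says only "An interim analysis is planned when approximately 50% subjects have completed 12 weeks of treatment", to guide further enrolment and the design of later trials. It names no test, interval or threshold. Taking n = 7, simulation gave 9.5%, 7.0% and 5.2% with 0, 1 and 2 values missing.

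**Conclusion.** The point holds in conditional form. If pooling follows SAP 8.4 without complete-data df, the main 95% CI of the primary endpoint is too narrow. For n = 15 it is about 9% too narrow with almost no missing information, where the two-sided error is about 7%. It is 11-14% narrower than the Barnard-Rubin interval at an assumed λ of 0.10-0.30. The actual error at n = 15 with 0-5 Week 12 values missing is about 5.5-7%, against about 3-4.6% with Barnard-Rubin df: modestly liberal against mildly conservative.

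These figures rest on three assumptions.

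- Exactly 15 subjects are analysed. Protocol 5.1 and 5.5 allow replacement, so the analysed number could differ.
- λ takes values that the documents do not give.
- The simulation represents the planned analysis. It is simplified: it imputes total scores at two visits, whereas the SAP imputes BWAT items using all visits.

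Severity is moderate. A reader might infer that the primary inference is invalid and must be repaired before anything else. The exploratory setting and the size of the simulated error do not support that.

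**What to change.** In SAP 8.4, state that MI results are pooled with small-sample (Barnard-Rubin) df and that the complete-data df equal the number of subjects analysed minus 1, passed to MIANALYZE through the EDF= option. Use the actual number in the analysis set, not a fixed 14. Apply the rule to BWAT, VAS and Wound-QoL, and to any subgroup or interim interval produced by MI, each with its own number of subjects.

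The cost is one option in the pooling step, with no new data and no change to what is estimated. Intervals become slightly wider and can be mildly conservative when several Week 12 values are missing. A footnote to the forest plot giving the df behind each row would let readers compare the rows fairly.
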